Study Number	AFT-25
Study Type/Phase	Interventional Phase III Randomized Clinical Trial
Clinical Indication	Low-risk ductal carcinoma in situ (DCIS)
ClinicalTrials.gov Identifier	NCT02926911
IND Number	Not applicable
Number of Trial Patients	1,080
Estimated Duration of Trial	Accrual: 78 months (07/01/16- 12/31/22) Follow up: 2-, 5-, 7- and 10-years
Rationale	To study the risks and benefits of active monitoring (AM) compared to surgery in the setting of a pragmatic prospective randomized trial for low-risk DCIS. Our overarching hypothesis is that management of low-risk DCIS using an AM approach does not yield inferior invasive breast cancer or quality of life outcomes compared to surgery.

Primary Objective	To assess whether 2-year ipsilateral invasive breast cancer rate for AM is non-inferior to that for surgery.
Secondary Objectives	To determine whether AM is non-inferior to surgery for the following outcomes: 2-, 5-, 7- and 10-year mastectomy rate, breast conservation rate, contralateral invasive breast cancer rate, overall survival and invasive breast cancer specific survival; health-related QOL, anxiety and depression at baseline, 6 months, 1 year, annually year 2-6, biannually thereafter; coping at baseline; intolerance of uncertainty at baseline and 2 years.
Trial Design and Schema	Multicenter Phase III Prospective Randomized Trial comparing surgery to active monitoring with option of endocrine therapy (in both arms) for low-risk ductal carcinoma in situ (DCIS) (see Study Schema below)

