4 METHOD OF TREATMENT ASSIGNMENT

4.1 Stratification Factors

Randomization will be stratified based on the following factors: **age at diagnosis**: <55, 55-65, >65; **maximum diameter of microcalcifications**: <2cms, 2-5cms, >5cms; DCIS nuclear **grade**: I or II. We will collect whether the patient has had prior surgical excision for the index diagnosis; this variable will be used for subset analysis and not stratification.

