4.2 Treatment Assignment

The study is designed to provide a 1:1 randomization of all patients to surgery or AM.

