10.2 Sample Size, Accrual Time and Study Duration

Power and Sample Size Considerations. Sample size for this study was estimated using a 2-group test of non-inferiority of proportions, with the 2-year invasive breast cancer rate in the surgery group assumed to be 0.10 based on published studies.^{61,62} The non-inferiority margin assumed was 0.05. Based on a 1-sided un-pooled z-test, with alpha=0.05, a sample size of n=446 per group will have 80% power⁶⁴ to detect the specified non-inferiority margin. The proportion of patients who decline the arm to which they are specifically randomized can diminish the estimate of treatment difference, and could also widen the confidence bounds, but the analytical approaches proposed here aim to diminish the impact on bias of the treatment difference. With a 3-year duration of accrual and 2 additional years of follow-up, we anticipate approximately 148 total events.

Analysis of Primary Outcome (See below for outcomes definitions). This trial was designed anticipating non-acceptance of arm allocation, and the proportion of patients that do not accept their arm allocation can lead to bias in estimates of treatment differences. Thus, we plan to complete several analyses of the primary outcome, reporting the primary intent to treat (ITT) analysis as well as sensitivity analyses that are intended to reduce the bias in estimation of treatment difference in this setting.

We assume that a clinically acceptable difference in 2-year invasive cancer diagnosis rate in order to conclude non-inferiority is 5%. Cumulative incidence curves will be used to estimate the invasive cancer diagnosis rates over time, and at the 2-year point, the difference in rates will be estimated and a 1-sided upper confidence bound of (AM-GCC) will be computed, using methods described by Austin.⁶⁵ We will conclude that AM is not inferior to Surgery if the upper confidence bound on the risk difference at 2 years is less than 5%.

ITT Analysis. The ITT analysis of 2-year invasive cancer diagnosis rate will be conducted using all patients, as randomized, and will be completed using Kaplan-Meier estimates, stratified by group, combined with the Greenwood's confidence interval. The difference in invasive cancer risks will be computed from the Cox model with treatment at 2 years, with a 1-sided 95% confidence interval of the difference (AM-GCC) computed.

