Participant subgroups and planned subgroup analyses. We hypothesize that both clinical outcomes and PRO measures may be dependent upon treatment arm and patient characteristics. Pre-specified subgroups for assessment of heterogeneity of treatment effect will include (1) **endocrine therapy** (yes/no as well as duration of therapy); (2) **choice of surgery** (lumpectomy or mastectomy); (3) **receipt of radiation** (yes/no); (4) **mode of monitoring** (q 6 month MMG versus additional imaging, i.e. ultrasound or MRI); (5) **race** (African-American women compared to white women; other minorities will also be assessed for HTE, but precision is likely to be low); (6) **menopausal status** (pre-or post-menopausal, as reported by the patient); (7) **baseline risk of invasive breast cancer** based on modified Gail Score; (8) **burden of comorbidities** at diagnosis which will impact the magnitude of clinical benefit derived from surgery for DCIS. These subgroup analyses will be completed using methods described by Austin⁶⁵ to estimate the average treatment effect (ATE) and the average treatment effect for the treated (ATT), using adjusted Cox models. The ATE would answer the question about how outcomes would change if a policy was instituted that all patients eligible for either therapy were only offered the “experimental therapy”, which here is Active Monitoring. We also consider the use of time-dependent methods for endocrine therapy and receipt of radiation therapy, using the Austin approaches as well, with time-dependent covariates in the Cox models.

Definitions of outcomes

Subsequent local breast events (SLBE) events are coded as one of the following types:

- **iINV:** Ipsilateral invasive in-breast cancer (includes chest wall recurrence)
- **iCIS:** Ipsilateral in situ in-breast cancer
- **cINV:** Contralateral invasive in-breast cancer (includes chest wall recurrence)
- **cCIS:** Contralateral in situ in-breast event cancer
- **iLX:** Ipsilateral lymph node cancer
- **cLX:** Contralateral lymph node cancer

Distant breast cancer metastasis (DistMet) is the only non-SLBE breast event considered

Ipsilateral invasive breast event is defined as first occurrence of either of the following:

- (i) *ipsilateral invasive breast cancer*,
- (ii) *ipsilateral lymph node cancer in the absence* of a preceding ipsilateral invasive breast cancer event,

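### The subgroup plan aims to assess heterogeneity of treatment effect, but the only method it names estimates average effects and specifies no comparison between subgroup levels

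*Combined protocol and SAP*

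**What the plan says.** The subgroup paragraph of Section 10.2 opens with its purpose: "Pre-specified subgroups for assessment of heterogeneity of treatment effect will include" eight factors. These are endocrine therapy, choice of surgery, radiation, mode of monitoring, race, menopausal status, baseline invasive cancer risk by modified Gail score, and comorbidity burden at diagnosis. The method given is "to estimate the average treatment effect (ATE) and the average treatment effect for the treated (ATT), using adjusted Cox models". Time-dependent covariates are considered for endocrine therapy and radiation. The question attached to the ATE is a policy question: what would happen if every eligible patient were offered AM only.

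Neither this paragraph nor any other section gives a treatment-by-factor term, a contrast between levels, a multiplicity rule or an exploratory label. The only caution about precision concerns minorities other than African-American women within the race factor. No subgroup sizes are given, and no cut points for Gail score or comorbidity.

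Section 4.1 says "Randomization will be stratified based on the following factors": age, maximum diameter of microcalcifications and nuclear grade. None of the three is among the eight. Section 10.2 states the 5% decision rule for the overall AM-minus-surgery difference at 2 years and gives no rule for subgroups.

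**The concern.** Heterogeneity is a statement about differences: whether the effect of AM at one level of a factor differs from its effect at another. The ATE and ATT differ from each other only in the population averaged over (everyone, or those treated). Computing either one separately by level gives a row of estimates but no comparison between them.

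Section 1.4 makes learning for which patients AM is favorable one of the criteria for choosing endpoints, so readers will look to these analyses for guidance. Without a planned contrast, the natural habit is to read each level alone, perhaps against the only bound in the document. A level can miss that bound simply because it is small. A patient group could then be described as unsuited to AM without evidence that the effect differs there.

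This point concerns the 2-year invasive cancer outcome, although the paragraph also mentions patient-reported outcomes.

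**Working it through.** **Inputs.** Section 10.2: "with the 2-year invasive breast cancer rate in the surgery group assumed to be 0.10 based on published studies"; "The non-inferiority margin assumed was 0.05"; "Based on a 1-sided un-pooled z-test, with alpha=0.05, a sample size of n=446 per group will have 80% power". Section 4.2: "The study is designed to provide a 1:1 randomization of all patients to surgery or AM". The synopsis gives 1,080 patients, so 1,080/2 = 540 per arm. Results are shown for both 446 and 540 per arm. Subgroup sizes are assumptions.

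**1. The plan's own figure.** n = (1.645 + 0.842)² × 2 × 0.10 × 0.90 / 0.05², which rounds up to 446 per group. Power at 446 is 80.1%. The figure reproduces.

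**2. Reading one level against the overall bound.** Assume a true difference of 0 and a rate of 10% in both arms. For n per arm in the level, SE = √(2 × 0.09/n) and P(bound below 5%) = Φ(0.05/SE − 1.645).

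- n = 223 (half of 446): SE 2.84 points, pass 0.546, miss 45.4%.
- n = 270 (half of 540): SE 2.58 points, pass 0.615, miss 38.5%.

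| Share of each arm (assumed) | Miss, 446/arm | Miss, 540/arm |
|---|---|---|
| 50% | 45% | 38% |
| 30% | 61% | 56% |
| 20% | 70% | 66% |
| 10% | 80% | 78% |

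A binomial simulation gave about 45% and 38% for the half-size level. In simulated trials that met the bound overall, at least one of the two levels of a 50/50 factor missed it in 62% (446 per arm) and 56% (540 per arm).

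**3. What a between-level contrast could show.** For a 50/50 factor the contrast is the difference between two risk differences, with SE = √(4 × 0.09/n), n per arm in each level, and two-sided alpha 0.05.

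| | 446/arm | 540/arm |
|---|---|---|
| SE | 4.0 points | 3.7 points |
| Power for a 5-point difference, Φ(0.05/SE − 1.96) | 24% | 28% |
| Detectable with 80% power, (1.96 + 0.842) × SE | 11.3 points | 10.2 points |

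With independent tests at 0.05 and no true heterogeneity, the chance of at least one false positive is 1 − 0.95⁴ = 19% for four factors and 1 − 0.95⁷ = 30% for seven.

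**4. Why the scale must be named.** Under one common hazard ratio (HR), the risk difference at baseline risk b is 1 − (1 − b)^HR − b. With HR 1.3 it is 1.5, 2.8 and 5.2 points at b = 5%, 10% and 20%. With HR 1 it is 0 throughout. The same data can therefore show no interaction on the hazard scale and a real one on the absolute scale. A model that fixes one hazard ratio imposes this pattern without estimating it.

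**5. Which factors allow a contrast.** Race, menopausal status, Gail risk and comorbidity burden at diagnosis are baseline factors. Endocrine therapy, choice of surgery, radiation and mode of monitoring are settled after randomization. The notes to Table 1 confine surgery and radiation to the surgery arm, and Section 6.1.1 confines 6-monthly mammography to the AM arm. Three of these four factors thus belong essentially to one arm, and no interaction term can repair that.

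**The case against.** Several parts of the case on the other side stand.

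- **No subgroup rule exists.** A reader might infer that the plan will generate subgroup failures. The documents do not support that: they apply the 5% bound only to the overall comparison. The miss rates describe a reading that the plan neither instructs nor rules out, at assumed subgroup sizes.
- **Interaction terms are not excluded.** An adjusted Cox model may contain them, and the cited methods paper is not available here. This is a method under-specified for its aim, not a decision against testing heterogeneity.
- **A built-in artifact is not shown.** It is tempting to say that the Cox approach manufactures heterogeneity. The text does not say that one common hazard ratio will be imposed. The spread also requires a hazard ratio different from 1, and it is then a true difference in absolute effect. Moreover, HR 1.3 at a 10% surgery rate means a 2.8-point overall difference, which meets the bound only about 31% of the time at 540 per arm. It does not picture a successful trial misled by its subgroups.
- **The ATT is not shown to be wrong.** As randomized, with 1:1 allocation, ATE and ATT nearly coincide in expectation. But Section 10.2 expects patients to decline their arm, plans as-treated and complier analyses, and does not restrict the subgroup models to treatment as randomized.
- **Stratification factors need not be subgroup factors.** The list is not closed, and Sections 4.1 and 10.3 already add prior excision for subset analysis. Including age, extent and grade is an inexpensive improvement, not the correction of an error.

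None of this supplies the missing comparison between levels.

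**Conclusion.** The point holds as a gap between aim and method. The plan promises an assessment of heterogeneity and names only average effects, with no contrast between levels. If levels were read singly against the overall bound, a half-size subgroup would miss it about 38 to 45% of the time with no true difference, and smaller ones more often. This assumes a 10% rate in both arms, an unpooled z-test and the stated subgroup shares.

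A proper contrast answers the right question but weakly: 24 to 28% power for a 5-point difference in effect at best balance, and about 10 to 11 points detectable with 80% power. That argues for estimation with intervals and an exploratory label, not for subgroup decisions. The change should be made before the subgroup analyses are run. It does not touch the primary conclusion.

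**What to change.** Amend the subgroup paragraph of Section 10.2 as follows.

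1. For race, menopausal status, modified Gail risk and comorbidity burden, plus age, extent of microcalcifications and grade, estimate the 2-year AM-minus-surgery risk difference within each level. Analyze as randomized, from Kaplan-Meier or cumulative incidence estimates, without imposing a common hazard ratio. Fix cut points and reference levels in advance.
2. Report the difference between levels in these risk differences (interaction on the absolute scale) with a confidence interval.
3. Label the analyses exploratory, state the low precision with the figures above, and say that the 5-point margin is not applied within subgroups.
4. Move endocrine therapy, choice of surgery, radiation and mode of monitoring to a separate descriptive or causal analysis with its own stated estimand. The ATT may be kept there.

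The cost is SAP wording and modest extra programming. The stratification factors are already recorded, so no new data are needed. The downside is a larger number of contrasts, which the exploratory label covers. The primary analysis and sample size stay as they are.

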2.2 Secondary Objectives

2.2.1 Quality of life and psychosocial outcomes:

The secondary hypothesis is based upon a non-inferiority endpoint that **2-, 5-, 6, 8, 10 health-related quality of life, rate of anxiety, and rate of depression are not inferior in the AM group compared to the surgery group.**

2.2.2 Clinical outcomes:

The secondary hypothesis is based upon a non-inferiority endpoint that **2-, 5-, 7- and 10-year rates of mastectomy, contralateral invasive breast cancer, and survival (both overall survival and invasive breast cancer-specific survival) are not inferior in the AM group compared to the surgery group.**

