Planned subgroup analyses (NCDB Special Study). The large DCIS registry developed through collaboration with the National Cancer Database (NCDB) will allow for the continued collection of long-term outcomes for patients as well as for the comparison of primary and secondary outcomes (when measurable in NCDB) for **AM versus surgery** amongst those patients who are randomized and accept their arm allocation versus those patients who are randomized but do not accept their arm allocation versus patients not registered or randomized to COMET, but who generally meet our broad inclusion criteria for the trial. Patients will be identified from all study sites during the time interval of COMET accrual. These analyses will be from predominantly non-randomized patients, so we plan to utilize observational study approaches for analyses. We will use full regression models (logistic or Cox model, dependent upon outcome measure) to control for potential confounders, including pathology, age, race, academic versus community setting, among others. As in other analyses, we will utilize inverse-probability weighting to handle missing data.⁷⁰

Analyses of long-term outcomes. Analyses of long-term outcomes will follow the approaches outlined above, modifying the year of rate calculations, accordingly. PRO data will utilize longitudinal linear mixed models over time, following appropriate scoring and transformation, if needed.

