10.5 Supplementary/Secondary Analysis Plans

Planned Analysis for PRO data: For analyses of PRO endpoints, we will use t-tests and ANOVA to compare unadjusted mean scores for health-related PRO measures at baseline. We will use linear mixed-effects models to assess change in these domains over time. Among women who are allocated to surgery, we will examine differences by surgery type (e.g., lumpectomy followed by radiation vs. unilateral mastectomy vs. bilateral mastectomy) and compare changes between these groups over time. In addition to baseline disease and socio-demographic data, information relating to other treatment (e.g., endocrine treatment, radiation) as well as co-morbidities will allow us to control for potential confounding by these factors. We will also analyze the decision-making, DCIS knowledge, and risk perception data at baseline and compare these domains between the surgery and AM groups. We plan to measure risk perceptions and knowledge again at 2 years and will assess change between the two time points in each group using t-tests (e.g., for continuous scores) and McNemar's test (e.g., proportion correctly perceiving their risk).

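### Secondary outcomes are posed as non-inferiority questions, but the only margin is 5 points for the 2-year invasive cancer rate; if it carries over, as Section 10.2 implies, it is too lenient for breast-cancer death

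*Combined protocol and SAP*

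**What the plan says.** The synopsis introduces the secondary objectives with "To determine whether AM is non-inferior to surgery for the following outcomes" and then lists mastectomy, breast conservation, contralateral invasive cancer, overall and breast-cancer-specific survival, and several patient-reported outcomes. Section 2.2 repeats the framing ("The secondary hypothesis is based upon a non-inferiority endpoint that"). Section 2.2.1 applies it to patient-reported outcomes: "health-related quality of life, rate of anxiety, and rate of depression are not inferior in the AM group compared to the surgery group". Section 2.2.2 applies it to mastectomy, contralateral invasive cancer and "survival (both overall survival and invasive breast cancer-specific survival) are not inferior in the AM group compared to the surgery group", at 2, 5, 7 and 10 years.

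One margin appears, in Section 10.2: "The non-inferiority margin assumed was 0.05". Its justification names one quantity: "We assume that a clinically acceptable difference in 2-year invasive cancer diagnosis rate in order to conclude non-inferiority is 5" per cent. The decision rule there is that the one-sided upper confidence bound on the risk difference (AM minus surgery) at 2 years lies below 5%.

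For later time points the same section says: "Analyses of long-term outcomes will follow the approaches outlined above, modifying the year of rate calculations, accordingly". Table 3 puts disease-specific and overall survival in the same Kaplan-Meier and Cox framework as the invasive breast event. Patient-reported outcomes are handled separately, at the end of Section 10.2 and in Section 10.5: "We will use linear mixed-effects models to assess change in these domains over time".

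**The concern.** A non-inferiority hypothesis cannot be tested without a margin. For the clinical secondary outcomes the reader is sent to the primary approach with a different year, and the only decision rule found there is the 5-point one. Five points was chosen against an assumed surgery-arm rate of 10%, where it allows a true ratio of 1.5 (15% vs 10%). For an outcome with a risk of a few per cent or less, the same absolute margin allows a much larger ratio.

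For the patient-reported outcomes the gap is different: Section 2.2.1 poses non-inferiority and speaks of rates of anxiety and depression, but the planned analysis models change in scores and has no margin or decision rule.

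Survival is where this matters most. Section 1.6 concedes that the low risk thought to follow from delayed diagnosis of invasive cancer has not been definitively shown. A statement that breast-cancer-specific survival is not inferior would be read as filling that gap, whether or not the margin behind it could support the reading.

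**Working it through.** **Inputs from the document.** Margin 0.05, one-sided alpha 0.05, unpooled z-test, surgery-arm rate 0.10, 446 per group, 80% power (Section 10.2). Planned enrolment 1,080 (synopsis) with 1:1 allocation (Section 4.2), hence 1,080 / 2 = 540 per arm. Background mortality in one trial of surgically treated DCIS: 2% breast-cancer deaths and 11% deaths overall, length of follow-up not given (Section 1.2.2).

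**Assumed.** The document gives no breast-cancer death rate for this trial, so surgery-arm risks of 0.5% to 3% are used. Simple proportions stand in for Kaplan-Meier or Cox estimates, and follow-up is complete. The results depend on the cumulative risk at the time point analysed, so they can be read at any of the planned years.

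**Step 1: the plan's own figure.** n = (1.645 + 0.842)² × (0.10 × 0.90 + 0.10 × 0.90) / 0.05² = 6.18 × 0.18 / 0.0025 ≈ 445.2, rounded up to 446. The stated size reproduces exactly.

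**Step 2: the same rule on breast-cancer death.** Declare non-inferiority if

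p₁ − p₀ + 1.645 × √[p₀(1 − p₀)/n + p₁(1 − p₁)/n] < 0.05,

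with p₀ the surgery-arm and p₁ the AM proportion. For 2% vs 4% at n = 446 the square root is √[(0.0196 + 0.0384)/446] = 0.0114, so the bound at the expected values is 0.02 + 1.645 × 0.0114 = 0.0388, which passes.

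**Step 3: chance of passing**, by summing over all pairs of binomial counts that satisfy the rule:

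| True risk, surgery vs AM | Ratio | 446 per arm | 540 per arm |
|---|---|---|---|
| 0.5% vs 2.5% | 5 | 96% | 98% |
| 1% vs 2% | 2 | over 99% | over 99% |
| 1% vs 3% | 3 | 92% | 95% |
| 1% vs 4% | 4 | 61% | 67% |
| 2% vs 4% | 2 | 83% | 88% |
| 2% vs 5% | 2.5 | 51% | 56% |
| 2% vs 6% | 3 | 21% | 23% |
| 2% vs 8% | 4 | 1% | 1% |
| 3% vs 6% | 2 | 43% | 48% |
| 3% vs 9% | 3 | 1% | 1% |

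In observed counts near 2%, the largest excess that still passes is 9 vs 22 deaths of 446 (ratio 2.4) or 11 vs 27 of 540 (ratio 2.5). On the margin itself, 2% + 5 points = 7%, a ratio of 3.5 against the 1.5 allowed for the primary endpoint.

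**Step 4: a commoner outcome for contrast.** With 11% deaths in both arms the rule passes in 77% of trials at 446 per arm and 84% at 540; with 11% vs 13% it passes in 40% and 45%. At that level the rule is not lenient.

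**The case against.** The strongest reply is that the plan never says 5 points applies to survival. Section 10.2 ties the margin to the 2-year invasive cancer diagnosis rate, and the sentence on long-term outcomes speaks of approaches, which can be read as the estimation methods (cumulative incidence, Cox-based risk differences, intent-to-treat with sensitivity analyses) without the decision rule. This stands: carry-over is implied, not explicit. It does not rescue the plan, because on that reading the secondary non-inferiority hypotheses have no margin at all and the choice stays open until data are in hand.

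A reader might also infer more than the document supports:

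- *Every secondary outcome is judged by the 5-point rule.* Patient-reported outcomes are expressly sent to mixed models.
- *A several-fold excess of breast-cancer death would be declared not inferior.* That depends on the control risk, which the plan does not assume. At 2% a tripling usually fails. Ratios of three or more pass reliably only at lower risks, such as a tripling at 1% or a fivefold excess at 0.5%.
- *Five points exceeds the whole expected rate of these outcomes.* The background figures of 11% overall deaths (Section 1.2.2) and 23.8% mastectomy (Section 1.1.2) contradict this as a general statement.
- *Non-inferiority on mastectomy is automatic.* No mastectomy rate is assumed for AM. At 23.8% in both arms the rule passes in 54% of trials at 446 per arm and 61% at 540; if AM were at 10% it would pass almost always. AM patients can reach surgery after invasive progression or by choice (Sections 5.2.2.1 and 10.7), and intent-to-treat keeps them in their arm.

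Finally, setting a margin for each outcome in advance would close the gap as well as dropping the claims would. That is fair, and the change proposed here leaves room for it.

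**Conclusion.** The concern holds in a limited form. No secondary non-inferiority hypothesis has a margin of its own. For clinical outcomes the text implies that the primary rule is reused; for patient-reported outcomes there is neither a margin nor a non-inferiority test. If the 5-point rule is used for breast-cancer death, a true doubling would usually pass at surgery-arm risks of 2% or less, and a tripling would usually pass at 1% but not at 2%. The weakness is confined to rare outcomes.

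These sizes rest on assumed control risks, one background figure with no stated follow-up time, and complete follow-up. Censoring would widen the bound and lower the chance of passing. That the secondary hypotheses lack margins of their own does not depend on any of these assumptions.

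**What to change.** In Section 10.2, state that the 5-point margin and its decision rule apply only to the 2-year primary endpoint, and that the sentence on long-term outcomes refers to estimation methods. In the synopsis and Sections 2.2.1 and 2.2.2, replace the non-inferiority wording with estimation: between-arm differences with two-sided 95% confidence intervals at 2, 5, 7 and 10 years for clinical outcomes, and at the planned survey times for patient-reported outcomes. Keep a non-inferiority claim only for an outcome that has its own margin, justified and fixed before that outcome's data are seen.

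This is a wording change; sample size, visits and patient care are unaffected. The cost is that the sponsor gives up formal secondary non-inferiority claims wherever no such margin is set.
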